| Secondary Objective(s) | | | |
| Research Intervention(s)/Interactions | 2 mg/kg, 1 mg/kg, 0.5 mg/kg, 0.25 mg/kg, 0.125 mg/kg of sugammadex and placebo | | |
| Study Population | Aged 18 years and above Scheduled to undergo an elective surgery in the main operating room or outpatient surgery center at Grady Memorial Hospital, Receive general anesthesia (standardized to sevoflurane for maintenance), Receive rocuronium for NMB, Receive neostigmine for NMB reversal, and Achieve a TOF count of at least 3 twitches but not a TOF ratio of 0.9 fifteen minutes after neostigmine has been given. | | |
| Sample Size | 36 | | |
| Study Duration for individual participants | 1 day (from start of surgery until PACU discharge) | | |
| Study Specific Abbreviations/ Definitions | NMB: neuromuscular blockade PACU: post anesthesia care unit TOF: train of four | | |
| Funding Source (if any) | Georgia CTSA (Clinical & Translational Science Alliance) pilot grants program | | |

Page 3 of 30 Version: 3 (10/14/2024)

2. Objectives

Objective: To determine what is an appropriate dose of sugammadex as rescue therapy following inadequate reversal with neostigmine.

Hypothesis: That a lower dose of sugammadex than currently recommended by the manufacturer is enough to achieve adequate reversal following neostigmine.

3. Background

Neuromuscular blocking agents (NMBAs) are commonly used in the practice of anesthesiology for skeletal muscle relaxation to facilitate tracheal intubation, mechanical ventilation, and to provide optimal surgical conditions. They fall into two categories, i.e. the non-depolarizing agents versus succinylcholine, which is the only depolarizing agent in clinical use. Non-depolarizing NMBAs in turn are classified as either an aminosteroid or benzylisoquinolinium compound; the former include pancuronium, vecuronium, and rocuronium, whereas the latter include atracurium, cisatracurium and mivacurium (1). In order to prevent residual NMB, it is vital to adequately reverse any use of a non-depolarizing NMBA. This was historically done using an anticholinesterase such as neostigmine, which would increase the concentration of acetylcholine at the neuromuscular junction leading to the return of neuromuscular transmission.

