Carvalho *et al.* conducted a meta-analysis of 53 studies (12,664 adult patients), where the pooled residual NMB incidence ranged from 0.115 when quantitative neuromuscular monitoring was used to 0.331 where no neuromuscular monitoring was used (7). Raval *et al.* conducted a meta-analysis of 20 randomized controlled trials (1,923 adult patients), where residual NMB (TOF ratio < 0.9) was found in 2.8% of patients who received sugammadex compared to 39% of those who received neostigmine 15 minutes post administration for a moderate block (TOF count 1-4) compared to 1.1% for sugammadex versus 99.1% for neostigmine 15 minutes after administration for a deep block (PTC 1-5) (8). Concerningly, 60 minutes after administration, 2.1% of the sugammadex group versus 19% of the neostigmine group still had NMB in the moderate block group compared to 0.4% of the sugammadex group versus 39.3% of the neostigmine group in the deep block group. When expanded to observational studies (58 studies with 25,277 adult patients), the incidence of residual NMB (TOF ratio < 0.9 upon arrival to PACU) ranged from 0% to 90.5% (median 30%), which was significantly lower (0% to 16%) in the sugammadex group compared to 3.5% to 90.5% in the neostigmine group and 15% to 89% in the spontaneous recovery group (9).

The incidence of residual NMB in the pediatric population has been variably reported. Ledowski *et al.* published in 2015 a series of 64 children (average age 8.2 years) who received NMBA for tracheal intubation, only 33 of whom received NMB reversal (32 with neostigmine 0.08 mg/kg and 1 with sugammadex); 19.4% of those who received no reversal and 37.5% of those who received neostigmine was found to have residual NMB (TOF ratio < 0.9) prior to extubation using acceleromyometry, giving an overall incidence of 28.1% (10). Similarly, Klucka *et al.* published in 2019 a series of 291 children (range: 29 weeks to 19 years of age) who received NMBA for surgery, 68 of whom received NMB reversal; the TOF ratio was found to be < 0.9 in 48.2% of patients prior to extubation in the OR versus 26.9% upon arrival to the PACU using accelerometry (11).

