Due to the high cost of sugammadex, some researchers have hypothesized that a lower dose is required when combined with neostigmine. A 2015 study from Beirut in adults undergoing elective surgery demonstrated that a dose of 2 mg/kg of sugammadex combined with neostigmine 0.05 mg/kg was non-inferior to the standard dose of 4 mg/kg of sugammadex in reversing deep NMB, defined as returning from a TOF count of 0 to a TOF ratio of 0.9 within 5 minutes, with similar times to extubation as well as no cases of recurarization in the post anesthetic care unit (PACU) (16). Lobaz, Sammut and Damodaran reported in 2013 the use of sugammadex as rescue therapy for a 71-year-old patient with end stage renal disease who was unable to be weaned off the ventilator almost five hours after receiving a single 1.2 mg/kg dose of rocuronium. He had initially achieved a TOF of 4, was reversed with 2.5 mg of neostigmine 45 minutes after induction, but failed to maintain adequate spontaneous ventilation despite his TOF remaining at 4, and was transferred to the intensive care unit 3 hours post induction. There, his TOF steadily declined to 2, as a result of which he received a 6 mg/kg dose of sugammadex, causing him to be successfully extubated ten minutes later (17). It is similarly important to dose sugammadex appropriately; Carollo et al. published a case report in 2019 of an 8-month-old patient who had recurarization after a 4 mg/kg dose of sugammadex was given with a TOF count of 2/4, which fortunately resolved after a second 4 mg/kg dose of sugammadex (18).

Lastly, known common adverse effects of neostigmine include bradycardia, nausea and vomiting (19), while the use of sugammadex has been found to lead to nausea, vomiting, hypotension and headache in \geq 10% of patients (5). There have also been case reports of marked bradycardia possibly leading to cardiac arrest with the use of both agents.

Page 6 of 30 Version: 3 (10/14/2024)

4. Study Endpoints

Primary study outcome:

The time taken to achieve a TOF ratio of 0.9 after the use of the intervention drug versus placebo in a patient population that has already received neostigmine for NMB reversal.

Secondary study outcome:

The percentage of patients who achieve a TOF ratio of 0.9 within 1 minute, 2 minutes, 5 minutes, and 10 minutes.

Safety outcomes:

The incidence in PACU (measured in %) of:

- i. Nausea,
- ii. Vomiting,
- iii. Bradycardia²,
- iv. Tachycardia³, and
- v. Hypotension⁴.

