Assuming assumptions are valid, an increasing exponential regression model with random intercept will be fitted with Time of Four Ratio versus Time, stratified by the natural log of the five dose levels (modeled below). This translates to a slow response initially followed by a more rapid response later. The random intercept will allow for different initial TOFR values.

Page 9 of 30 Version: 3 (10/14/2024)

$$TOFR = \frac{1}{B}e^{(A+time)/B} + TOFR_{initial} + C * \ln(dose)$$

"Success" will be defined as TOFR of ≥0.9 within 5 minutes for 95% of patients, following the model estimate, adjusting for the 95% confidence intervals of the estimates, based on initial TOF ratios, which may be grouped as needed. A secondary analysis will be conducted by TOFC to determine optimal dose at each TOFC level, and if TOFC correlates strongly with TOFR.

8. Data and/or Specimen Banking

N/A

9. Sharing of Results with Participants

N/A

10. Study Timelines

All subjects are anticipated to participate in the study from the start of their surgery to the time of their discharge from the PACU, which should be on the same day. It is expected that 1 year would be required to enroll all study subjects, and for the study to be completed by July 2023.

11. Inclusion and Exclusion Criteria

Individuals will be screened for eligibility at the anesthesia pre-admission clinic.

Inclusion criteria:

- Patients aged 18 years and above who will
- Undergo an elective surgery in the main operating room or outpatient surgery center at Grady Memorial Hospital,
- Receive general anesthesia (standardized to sevoflurane for maintenance),
- Receive rocuronium for NMB,
- Receive neostigmine for NMB reversal,
- Achieve a TOF count of at least 3 twitches but not a TOF ratio of 0.9 fifteen minutes after neostigmine has been given, and
- Able and willing to provide informed consent.

Exclusion criteria:

Page 10 of 30 Version: 3 (10/14/2024)

- Pregnancy and/or lactating,
- BMI ≥ 40,
- Severe renal impairment, i.e. chronic kidney disease stages IV and V as defined by GFR < 30 ml/min/1.73 m² (21),
- Severe hepatic impairment, i.e. Child-Pugh score C⁵ (22, 23),
- Pre-existing neuromuscular disease,
- Anticipated need for postoperative intubation, and/or
- Known hypersensitivity reactions to rocuronium, neostigmine and/or sugammadex.

12. Population

We will not be including the following special populations:

- Adults unable to consent
- Individuals under the age of 18 years
- Pregnant women

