Data on serious adverse events such as death, perioperative cardiac arrest, and unplanned hospitalization as well as any other adverse events will also be collected up to the time of PACU discharge for both study participants as well as screen failures (participants who were recruited but not enrolled in the trial due to not fulfilling the study inclusion criteria).

Monitoring Table 3

| DSMP Requirement | How this Requirement is Met | Frequency | Responsible Party(ies) |
|---|--|---|---|
| Real-time review of participant data during | PI will review the data as it is being collected. | Every data collection | PI |
| initial data collection. | being conected. | timepoint | |
| | | Expectation is that this happens every | |
| | | time you obtain information. | |
| Site Monitoring at predetermined intervals: | There should be a standard operating procedure to review | Every 6 months | PI (self-assessment tool) |
| The Principal Investigator has a responsibility to ensure that the study is | data (whether a sample or 100%) at pre-determined intervals to ensure that there is | At a minimum, a review is required annually when no | Delegate a responsible party for each |
| following all aspects of the protocol. | adequate documentation of critical elements such as | one has been enrolled or the | requirement below. Self-assessment is |
| | eligibility criteria. Monitoring is required at the following | study is in long term follow up. | acceptable*. Self-assessment: a |
| | timepoints (but may be done more frequently): • study initiation • at least every six months | Additional risk- based interim monitoring may be required at least | process for self- assessment of protocol compliance and data integrity |
| | while participants are receiving intervention and | once every 12-24 weeks based on the site activity, to | which can be part of an overall DSMP. See CTAC's self- |
| | annually while participants are in follow-up | include the possibility of remote monitoring. | assessment tool on their webpage. |

Version: 3 (10/14/2024)

Page 16 of 30 IRB Form BIO 01192022

| | | A longer frequency | |
|---------------------------|--------------------------------------|-----------------------|--------------------|
| | | could be | |
| | | acceptable with | |
| | | justification about | |
| | | risk to participants. | |
| 100% review of | DCTR will review all regulatory | At study initiation | DCTR |

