| regulatory files | files at study initiation as well as | & annually | |
| | on an annual basis, either in | | |
| | electronic or paper form. | Reviewed at a | |
| | | minimum of first | |
| | | and close-out visits | |
| 100% review of consent | DCTR will review all consent | Every month | DCTR |
| forms | forms on a monthly basis. | | |
| Review of credentials, | DCTR will review the credentials | At study initiation | DCTR |
| training records, the | of all study personnel at study | & annually | |
| delegation of | initiation and on an annual | | |
| responsibility logs (if | basis. | | |
| applicable) | | | |
| Comparison of case | PI will compare CRF to the | Every month | PI |
| report forms (CRF) to | source documentation in the | | |
| source documentation | patient's Epic charts on a | | |
| for accuracy and | monthly basis. | | |
| completion | · | | |
| Review of | PI will review all adverse events | Every month | PI |
| documentation of all | as reported on a monthly basis. | | |
| adverse events | | | |
| Monitoring of critical | PI will monitor all critical data | Every month | PI |
| data points (eligibility, | points on a monthly basis. | | |
| study endpoints, etc.) | | | |
| Laboratory review of | N/A | N/A | N/A |
| processing and storage | | | |
| of specimens | | Reviewed at first | |
| | | and close-out visits | |
| | | and at least | |
| | | biannually | |
| Assessment of laboratory | N/A | N/A | N/A |
| specimens stored locally | | | |
| Test article | Grady Pharmacy IDS will review | Every 6 months | Grady Pharmacy IDS |
| accountability review | the study drug accountability | | |
| | records at least every 6 months. | Reviewed at first | |
| | | and close-out visits | |
| | | and at least | |
| | | biannually | |

Version: 3 (10/14/2024)

| Accountability logs, | Grady Pharmacy IDS will review | Every 6 months | Grady Pharmacy IDS |
|---------------------------|---------------------------------|---------------------|--------------------|
| dispensing records, and | the study drug records at least | | |
| other participant records | every 6 months. | At least biannually | |
| For FDA regulated | | Timing, frequency, | |
| studies, the following | | and intensity of | |
| requirements apply: | | monitoring | |
| Monitoring methods | On-site & Self-assessment | Every 6 months | PI |
| (may include centralized, | | | |
| on-site, and self- | | | |
| assessment) | | | |

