^{*}For international studies, you are required to engage a CRO that is working in the site country and/or to consult with Emory's legal counsel regarding compliance with the country's clinical research regulations.

DCTR: Emory University Department of Anesthesiology Division of Clinical and Translational Research staff member

IDS: Investigational Drug Services

PI: Principal Investigator

22. Provisions to Protect the Privacy Interest of Participants

The research procedures are not beyond what is routinely used in a patient's intraoperative and postoperative anesthetic management. The patient will be given the option to not interact with study team members whenever he/she is not comfortable. The research team will contact the subject up to the time of discharge from the PACU, and only beyond that if necessary (e.g. if there is a significant adverse event that may or may not be related to the study).

23. Economic Burden to Participants

N/A

24. Informed Consent

We will be informing and consenting patients in the anesthesia pre-admission clinic. This consent will be checked on the day of surgery itself to ensure ongoing consent. The principal investigator will be the one consenting study participants. Study subjects will be informed that participation in the study has no bearing on their clinical care, and will be given the opportunity to withdraw from the study at any time point.

The consent form has been attached to this protocol.

25. Setting

This is a single-site study at the Grady Memorial Hospital. Potential participants will be identified and recruited at the anesthesia pre-admission clinic on site. Research procedures will be performed in the main operating room and ambulatory surgery center on site.

Page 18 of 30 Version: 3 (10/14/2024)

26. Resources Available

The study drug and equipment required for the study are all in routine clinical use at the Grady Memorial Hospital. As the inclusion criteria are broad and there is an average of 20-30 cases per weekday of elective surgeries requiring tracheal intubation and NMB, we anticipate that there would be minimal problems in recruiting the required number of suitable subjects within the aforementioned recruitment period. We will be briefing the anesthesiology department staff prior to the study commencement on the details of this research study.

27. Multi-Site Research When Emory is the Lead Site

N/A

28. References

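### Serious events first arising after PACU discharge, including the named unplanned hospitalization, are not systematically ascertained

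*Combined protocol and SAP*

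**What the plan says.** Section 21 (data and safety monitoring) opens its list of serious events with "Data on serious adverse events such as death, perioperative cardiac arrest, and unplanned hospitalization", adds any other adverse events, and says that these data "will also be collected up to the time of PACU discharge for both study participants as well as screen failures".

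The other sections use the same end point:
- Section 1 gives individual study duration as "1 day (from start of surgery until PACU discharge".
- Section 10 has participation run "from the start of their surgery to the time of their discharge from the PACU, which should be on the same day".
- Section 20 places data collection by the study team in the operating room and the PACU. Its listed postoperative items are nausea, vomiting, bradycardia, tachycardia and hypotension.
- Section 22 says: "The research team will contact the subject up to the time of discharge from the PACU, and only beyond that if necessary". The example it gives is a significant adverse event.

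Two provisions in Section 6 bear on late block. A patient below a TOF ratio of 0.9 at 10 minutes is treated further until that threshold is reached and extubation is safe. The ratio is then measured again 30 minutes after PACU arrival to look for delayed residual block.

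Sections 4 and 20 make the patients who were recruited but not treated the comparison group for safety. Monitoring Table 3 already has a monthly check in which the "PI will compare CRF to the" source documentation in the Epic chart.

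**The concern.** Unplanned hospitalization can happen after the patient has left the PACU. Patients from the outpatient surgery center are eligible (Section 11), and inpatients are recruited as well (Section 15). An outpatient may go home and come back. An inpatient may deteriorate on the ward. Neither event falls inside the collection window, and nothing scheduled would bring it to the study team's notice.

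The matter is worth attention because the study is classed as more than minimal risk (Section 21) and tests whether less than the recommended dose is enough (Section 2). Section 5 describes 2 mg/kg as the lowest approved dose, so five of the six arms (four lower doses and placebo) lie below it. By Table 1 that is 5 × 6 = 30 of the 36 treated patients. No respiratory event appears among the listed postoperative items, so the serious-event paragraph is the main route by which such harm would be recorded.

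At stake is what a zero count means. A report of no unplanned hospitalization would mean none before PACU discharge, and readers could take it to mean none at all. The screen failures share the cut-off, so comparing the two groups does not reveal the gap.

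**Working it through.** The plan states no figure for this point, so the main check is to follow events through the text.

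**Step 1. Which events reach the data?**
- *Admission decided in the PACU:* inside the Section 21 window. Captured.
- *Residual block present 30 minutes after PACU arrival:* sought by the TOF re-check in Section 6. Captured.
- *Return to hospital after outpatient surgery:* after PACU discharge. Sections 1, 10, 20 and 21 have all closed. Section 22 permits contact if the event is known, but no visit, call or record review would find it. Not systematically ascertained.
- *ICU transfer, reintubation or death on the ward after PACU:* the same.

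The monthly comparison in Monitoring Table 3 checks form entries against the chart. As the forms cover the period to PACU discharge, the check does not by itself extend the window.

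**Step 2. How many patients?** Section 7 anticipates that 70% of those enrolled will not need treatment: 36 / (1 − 0.70) = 120 recruited, and 120 − 36 = 84 screen failures. Both 120 and 84 are upper limits, since the protocol says up to 120.

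**Step 3. What might go unrecorded?** The documents give no rate of serious events after PACU discharge, so the rates below are assumptions. The chance of at least one such event among n patients is 1 − (1 − p)^n.

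| Assumed rate p | 36 treated | 120 recruited |
|---|---|---|
| 0.3% | 10% | 30% |
| 1% | 30% | 70% |
| 2% | 52% | 91% |
| 5% | 84% | 99.8% |

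For example, 1 − 0.99^36 = 0.304.

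**Step 4. What could a longer window show?** With complete ascertainment and no events, the one-sided 95% upper limit is 1 − 0.05^(1/n). That is 8.0% for 36 patients and 39% for one arm of 6. A longer window would make the safety statement accurate. It would not support a comparison between doses, and Section 4 already says that the sample is too small for formal non-inferiority tests of safety.

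**The case against.** The strongest case against is that the window is deliberate and consistent. The safety outcomes in Section 4 are defined as incidence in the PACU, every section that mentions timing uses the same end point, and later contact is permitted. Patients in all arms are brought to a TOF ratio of 0.9, then re-checked, so late block should be uncommon. Most screen failures are expected to have recovered already, so residual block is scarcely an issue for them. All of this stands. It lowers the likely number of late events but gives no means of finding those that occur, and the documents give no reason for the cut-off.

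A reader might also infer more than the documents support:
- *That listing unplanned hospitalization contradicts the window.* It does not. An admission from the PACU is inside it; the listing is only incompletely served.
- *That the background case report shows the window closing before the period of risk.* In that report "There, his TOF steadily declined to 2" in intensive care, but the patient had end stage renal disease, which Section 11 excludes, and was visibly failing to breathe adequately before any PACU discharge could arise. The hours quoted run from induction or rocuronium, not from PACU arrival, and the protocol states neither surgery length nor PACU stay.
- *That the meta-analysis figure in Section 3 ("60 minutes after administration, 2.1% of the sugammadex group versus 19% of the neostigmine group still had NMB") shows block returning later.* It describes block persisting after neostigmine as the reversal agent. Here that group is identified at 15 minutes and treated. The planned re-check falls at up to about 15 + 10 + 30 = 55 minutes after neostigmine, plus transfer and any further treatment, so 60 minutes lies near the check and possibly within the PACU stay.
- *That late respiratory events are the harms most likely to separate the doses.* No section says so, and six patients per arm could not show it.

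**Conclusion.** The point holds as a gap in safety ascertainment. Serious events that first arise after PACU discharge are not systematically ascertained in the 36 treated patients or in up to 84 screen failures. It would be too strong to say that all later events are missed, because Section 22 lets the team follow up an event that comes to its notice.

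The primary endpoint, the sample size and the efficacy analysis are untouched. The size of the gap in events cannot be stated from the documents; the table in the working rests wholly on assumed rates. The conclusion itself rests only on the text, and on there being no further follow-up instruction in material not available here, such as the consent form or the data collection form. This is a cheap improvement to the plan rather than a flaw that threatens its main result.

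**What to change.** In Section 21, extend serious-adverse-event collection beyond PACU discharge by review of the hospital electronic record to a fixed point, for example the day after surgery or hospital discharge. The later of the two would be safer: for an outpatient, hospital discharge alone could close the window before any return. Use the same window for treated patients and screen failures. Count unplanned admission, return to hospital, ICU transfer, reintubation and death.

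Do the review at the existing monthly comparison of case report forms with Epic charts. This is a single-site study, and no added contact or procedure is needed. State the new window in Sections 1, 10 and 22 and in the consent form. If the sponsor keeps the present cut-off, justify it. Label any result limited to that window as covering events up to PACU discharge.

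The cost is an amendment, consent wording and a few minutes of chart review per patient, for at most 120 patients. More events unrelated to the drug will be listed, and admissions to other hospitals will still be missed, which the report should say.
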